8.1 Specification of Safety Parameters

8.2 Recording and Reporting of Adverse Events (AEs)

AEs will be reported by the subject (or, when appropriate, by a caregiver, surrogate, or the subject's legally authorized representative).

The investigator and any qualified designees are responsible for detecting, documenting, and recording events that meet the definition of an AE or Serious Adverse Event (SAE) and remain responsible for following up on AEs that are serious, considered related to the study intervention or study procedures, or that caused the subject to discontinue the study treatment or participation in the study.

8.2.1 Time Period and Frequency for Collecting AE and SAE Information

All AEs will be collected from the start of intervention until completion of all follow-up visits.

All SAEs will be collected from the start of intervention until completion of all follow-up visits.

Medical occurrences that begin before the start of study intervention but after obtaining informed consent must be recorded in the subject's medical record.

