2.1. Trial Rationale and Background

Bone metastases are the most common site of distant metastases and can cause severe and disabling effects, including pain, spinal cord compression and pathologic fracture^{1, 2}. These complications can greatly affect a patient's quality of life and cause immense suffering.

Radiotherapy (RT) is an effective treatment for palliative patients with painful bone metastases. It is also efficacious in preserving function and maintaining skeletal integrity, while minimizing the occurrence of adverse skeletal related events³. There is a significant amount of evidence showing that a single fraction (SF) of RT provides equivalent pain relief as multiple fractions (MF), which are associated with more acute toxicity, are less convenient for patients and costlier for the health care system^{1, 4, 5}. Therefore, SF-RT is encouraged, but 20 Gy in 5 fractions is also allowed in this study, though should be chosen only in patients with a complicated bone metastases by fracture, neurological deficit (e.g. spinal cord compression), or a large soft tissue component. In patients with advanced disease, management strategies focus on improving quality of life (QOL), rather than conventional endpoints such as survival⁶.

Rationale for Current Study

Currently, the standard of care in British Columbia for palliative patients with bone metastases is SUPR. In other jurisdictions, however, factors such as physician remuneration make other complex planning techniques more popular.

BC Cancer is publicly funded with no direct costs to patients. All RT in the province is provided by 6 centres where radiation oncologists receive an annual salary, which are independent of RT treatment technique and duration⁷. Due to the lack of financial incentive associated with a more complex RT plan, BC Cancer is a unique clinical setting to assess the use of VMAT versus SUPR⁷.

As facilities providing RT have gained more experience with VMAT and improvements to VMAT planning software have been made, the planning time required has been reduced⁸. Previously, approximately 2 weeks was required for a team at the BC Cancer to create a VMAT plan for a palliative patient with bone metastases; however, we hypothesize this can now be reduced to three days in settings with low dose prescription.

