This study will allow us to determine if there is reduced toxicity associated with VMAT compared to SUPR with only a modest impact on resources. Our hypothesis is that VMAT will have reduced toxicity compared with SUPR for palliative patients with bone metastases. We also hypothesize that there will be no difference between the two arms in terms of pain response, due to the fact that the doses are equal. This hypothesis is driven by the radiobiologic rationale, which defines effective RT as the ability of radiation to induce tumour cell death while sparing normal cells.

The importance in determining if there is any benefit in terms of toxicity with VMAT compared with SUPR for palliative patients with bone metastases is obvious when consequences related to its adoption are considered. As previously discussed, although the planning time has been drastically reduced, there is still an expected modest increase in resources required to carry out a VMAT plan. For patients, the pre-treatment process of VMAT is more burdensome, i.e. patients have to wait longer before receiving VMAT as compared to SUPR, due to the increased plan complexity. Therefore, it is important to consider the patient experience in relation to the RT administration.

In summary, evidence that either supports or refutes the hypothesis that VMAT will have reduced toxicity compared with SUPR for patients with bone metastases will be helpful in guiding future practices. We are not aware of any other randomized control trials (completed or ongoing) that have addressed this issue, though a London Ontario study is randomizing patients receiving palliative lung RT to SUPR vs VMAT⁹. Due to the implications of VMAT on departmental resources and patient experience, better evidence from a randomized control trial is required before the widespread use of this technique can be justified.

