2.2.2. Radiation therapy 2 – Volumetric Modulated Arc Therapy (VMAT)

In order to deliver 3D Conformal Radiotherapy, a CT simulation is used to develop the treatment plan. The goal is to deliver a conformal radiation dose to the target volume with maximal sparing

Protocol number v12.0; 16 Apr 2024

of the normal tissue. VMAT (Volumetric Modulated Arc Therapy is a type of 3D conformal RT, and delivers the radiation dose more conformally than SUPR, possibly reducing acute and late toxicity¹¹⁻¹³. The disadvantages of VMAT include more complex planning and quality assurance processes compared with SUPR5. The complex planning required can be time-consuming, which can have a significant impact on departmental resources, and the wait time for the patient.

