These toxicities must be documented in the AE log and SAE report form, and entered in REDCap, and follow REB and institutional reporting guidelines.

Note: The term “severe” is a measure of intensity: thus a severe adverse event is not necessarily serious. For example, nausea of several hours’ duration may be rated as severe, but may not be clinically serious.

Immediately Reportable Serious/Adverse Events

Any **Grade 4 or 5 serious adverse event** that is definitely, probably, or possibly the result of protocol treatment must be reported to the Study PI within 24 hours of discovery, and

Protocol number v12.0; 16 Apr 2024

further reported to the REB per institutional guidelines. The follow-up/final report should be completed within an additional 8 days. All other SAEs (Grade 2-3) that are definitely, probably, or possibly related to treatment should be reported to the Study PI within 15 days. These should be documented in an SAE Report form and in REDCap as well.

Unanticipated events are to be reported to the Study PI within 24 hours of discovery, and to the local REB as required.

Local and non-local SAEs will be reported to the applicable REB as per their reporting guidelines.

NOTE: Conditions that are NOT considered a SAE in this protocol are not included in reporting requirements, e.g., hospitalizations for routine procedures, disease progression, or death from disease progression

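### AE and SAE collection opens at the start of intervention rather than at randomisation, so formal safety data omit a wait that the protocol expects to be longer with VMAT; this probably favours VMAT, by an unknown amount

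*Combined protocol and SAP*

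**What the plan says.** Section 8.2.1 sets one window for both kinds of event. For AEs: "All AEs will be collected from the start of intervention until completion of all follow-up visits". For SAEs: "All SAEs will be collected from the start of intervention until completion of all follow-up visits". For anything between consent and that point: "Medical occurrences that begin before the start of study intervention but after obtaining informed consent must be recorded in the subject's medical record". The start of intervention is not defined; the first radiotherapy treatment is the natural reading. Events that qualify for reporting follow a different route under 8.2.2: "These toxicities must be documented in the AE log and SAE report form, and entered in REDCap".

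On the wait, section 2.1 says "patients have to wait longer before receiving VMAT as compared to SUPR, due to the increased plan complexity". It puts VMAT planning at about 2 weeks in the past and at a hypothesised three days now. Section 2.2.2 lists the drawbacks of VMAT: "The disadvantages of VMAT include more complex planning and quality assurance processes compared with SUPR5". It adds that the planning can be time-consuming, "which can have a significant impact on departmental resources, and the wait time for the patient".

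The general background in section 2.1 says that bone metastases "can cause severe and disabling effects, including pain, spinal cord compression and pathologic fracture". Section 9.1 analyses patients in their assigned groups. In the section 4.8 schedule, randomisation (Visit 1) comes before the first treatment (Visit 2, Day 1).

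**The concern.** The comparison between arms starts at randomisation, but formal safety data start at treatment. If the gap between the two were the same in both arms, little would be lost from the comparison. The protocol expects it to be longer with VMAT. A patient who is admitted, fractures a bone or dies after randomisation but before radiotherapy need not appear in the AE log, on an SAE form or in the REDCap safety data, and more VMAT than SUPR patient-time falls in that gap.

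Section 2.1 says that a randomised trial is needed before VMAT is widely used, because of what VMAT means for departmental resources and patient experience. Serious events while waiting bear on that question. The annual review by the safety committee (12.1.5) covers toxicity outcomes, so it would not see these events systematically.

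**Working it through.** No figure in the plan depends on the collection window, so there is nothing to reproduce. The argument is textual; the arithmetic only shows what scale is possible.

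**Step 1: the omitted interval.** Let w be the days from randomisation to the start of radiotherapy. Analysis counts from randomisation (9.1, 4.8) and collection from the start of intervention (8.2.1), so the omitted period is w. Section 2.1 implies that w is larger for VMAT.

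**Step 2: inputs.**
- Arm size: 250 patients at 1:1 (sections 1 and 3.2), so 125 per arm.
- VMAT wait: 3 days (hypothesised) or 14 days (the earlier practice), both from 2.1. These are planning times, used here as stand-ins for w.
- SUPR wait: not given; assumed 0 to 1 day.
- Daily probability r of a serious event before radiotherapy: not given; assumed 0.5% to 2%, equal in both arms.

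**Step 3: uncollected patient-days = 125 × w.**
- VMAT, 3 days: 125 × 3 = 375.
- VMAT, 14 days: 125 × 14 = 1,750.
- SUPR, 0 to 1 day: 0 to 125.

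**Step 4: uncollected share of the period from randomisation to week 4 = w / (w + 28), single-fraction schedule.**
- VMAT, 3 days: 3/31 = 9.7%.
- VMAT, 14 days: 14/42 = 33.3%.
- SUPR, 0 to 1 day: 0% to 1/29 = 3.4%.

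**Step 5: expected patients with an uncollected event = 125 × [1 − (1 − r)^w].**

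| Wait | r = 0.5% | r = 1% | r = 2% |
|---|---|---|---|
| SUPR, 0 days | 0 | 0 | 0 |
| SUPR, 1 day | 0.6 | 1.3 | 2.5 |
| VMAT, 3 days | 1.9 | 3.7 | 7.4 |
| VMAT, 14 days | 8.5 | 16.4 | 30.8 |

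With equal daily risk, the arm that waits longer loses more events. That direction follows from 2.1 and 8.2.1 under the equal-risk assumption. The sizes rest entirely on the assumed r and SUPR wait.

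**Step 6: what is captured elsewhere.**
- Time to treatment (3.1.2) gives the length of the wait, not events in it.
- The provider-assessed Baseline & Follow-up form (4.8) is repeated on Day 1 if radiotherapy starts 3 or more days after baseline. It covers symptoms and toxicity, and the patient must reach Day 1.
- BPI, FLIE and PROMS (4.8) need no Day 1 repeat if collected within 7 days, so a 3-day wait normally triggers none.
- The Study Termination form (11.3) gives the date and reason for discontinuation.
- Survival (9.1) feeds the QALY analysis.
- Unanticipated events (8.2.2) are reportable, including those possibly caused by taking part in the research.

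None of these gives a by-arm record of fractures, cord compressions, admissions and deaths before radiotherapy.

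**Step 7: would an earlier window be enough?** No. Section 1 limits reporting to events of grade 2 or higher that are at least possibly related to radiotherapy. Section 8.2.2 limits it to grade 2 or higher in treatment-related areas. Both leave disease progression, and death from it, out of SAE reporting. Most events from untreated metastases would still be dropped.

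**The case against.** The strongest case against the point has five parts.

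- **No clinical harm is predicted from the wait.** Section 2.1 calls the pre-treatment process more burdensome and raises patient experience. The fracture and cord compression wording is general background, and clinical cord compression is an exclusion. This stands. A reader might also take the wait to be the main drawback of VMAT, but 2.2.2 lists planning and QA complexity first, then resources and wait, without ranking them.
- **The start date is not the main filter.** This stands too: the relatedness and progression rules would remove most such events in either arm, even after treatment starts. It means that the fix must go beyond the window, not that the window is harmless.
- **No between-arm AE analysis is specified.** Section 9.1 gives only t-tests of average scores, and the stopping thresholds in 11.2 are not stated by arm. The primary endpoint, FLIE at day 5 after the start of radiotherapy, is untouched. This limits the consequence to the safety description and to the adoption question.
- **The wait is partly captured.** True, as step 6 shows, but in pieces that do not add up to a record of serious events by arm.
- **A remedy can bias the other way.** If all-cause events were counted only before radiotherapy, the arm that waits longer would collect more of them while later events stayed filtered. This is right, so one rule must apply before and after treatment starts.

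A reader might also infer that the repeated Day 1 form replaces the baseline, so that symptoms arising in the wait become baseline status. Section 4.8 has separate columns for the two visits and does not say this.

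**Conclusion.** The point holds as a gap in the safety record and a worthwhile, inexpensive improvement. Formal AE and SAE data omit a post-randomisation period that the protocol's own account makes longer for VMAT. The likely direction favours VMAT, if daily risk while waiting is similar in the two arms and start of intervention means the first treatment.

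The size is unknown. The 375 patient-days against 0 to 125 measure exposure, not harm, and the event counts rest on assumed rates. The 14-day figures use a planning time that section 2.1 describes as past practice. A reader might conclude that the safety result is biased by construction. The documents do not support that: they give no pre-treatment event rate and no SUPR wait, and they specify no between-arm AE test.

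**What to change.** 1. In 8.2.1, define the start of intervention.
2. Add to 8.2.1 a listing for both arms, from randomisation to the week 4 visit, of all SAEs, cord compressions, fractures, unplanned admissions and deaths, regardless of relation to radiotherapy or progression. Include patients who never start radiotherapy.
3. State that the grade, relatedness and progression limits in section 1 and 8.2.2 do not apply to this listing, before or after treatment starts, so that both arms are counted by the same rule.
4. Tabulate the listing by randomised arm beside time to treatment. The week 4 visit is timed from the last treatment, so a longer wait also lengthens this window. Give person-days of observation per arm, and fix an end date for patients who are never treated.
5. Keep the existing RT-related toxicity reporting, from the start of radiotherapy, as a separate table.
6. Reconcile the all-AE wording in 8.2.1 with the grade and relatedness limits in section 1 and 8.2.2.

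The cost is a short amendment, a REDCap form or field, and more disease-related events to log. Section 8.2.1 already requires occurrences between consent and treatment to be in the medical record, so most of the work is abstraction, which can also be done for patients already enrolled.

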8.2.2 Method for Detecting AEs and SAEs

Definitions

An *Adverse Event (AE)* is any unfavorable and unintended sign (including an abnormal laboratory finding), symptom, or disease temporally associated with the use of a medical treatment or procedure that may or may *not* be considered related to the medical treatment or procedure.

Serious Adverse Event (SAE) as defined in the ICH Guideline: Clinical Safety Data Management: Definitions and Standards for Expedited Reporting, E2A Section IIB includes any untoward medical occurrence that at any dose/treatment:

- Results in death
- Is life-threatening (refers to an event in which the patient was at risk of death at the time of the event; it does not refer to an event which hypothetically might have caused death if it were more severe.)
- Results in persistent or significant disability/incapacity
- Requires in-patient hospitalization or prolongation of existing hospitalization (excluding hospital admissions for scheduled elective surgery and admissions for palliative or terminal care)

- Is a congenital anomaly/birth defect

Important medical events that may not be immediately life-threatening or result in death or hospitalization may be considered a serious adverse event, when, based upon medical and scientific judgment, they may jeopardize the patient or may require intervention to prevent one of the other outcomes listed in the definition above.

Unanticipated/unexpected events include events that are inconsistent with, or present a greater risk of harm, than the known or recognized risks or side effects of SUPR or VMAT treatment as explained to the patient under standard of care. Unanticipated events also include those events where there is a reasonable possibility that the incident, experience, or outcome may have been caused by the procedures involved in the research (i.e. possibly, probably, or definitely related to participation in the research itself).

Expected events are distinguished from unexpected events on a case by case basis, at the discretion of the radiation oncologist.

Causality

An adverse event is considered **related** to the research intervention if there is a reasonable possibility that the event may have been caused by the research intervention (i.e. a causal relationship between the event and the research intervention cannot be ruled out by the investigator(s)).

The relationship of an AE to the study treatment (causality) will be described using the following definitions:

Unrelated: Any adverse event for which there is evidence that an alternative etiology exists or for which no timely relationship exists to the administration of the study treatment and the adverse event does not follow any previously documented pattern. The adverse event, after careful consideration by the investigator, is clearly and incontrovertibly due to causes other than the intervention.

Unlikely: Any adverse event for which the time relationship between the study treatment and the event suggests that a causal relationship is unlikely and/or the event is more likely due to the subject's clinical condition or other therapies concomitantly administered to the subject.

Possible: Any adverse event occurring in a timely manner after the administration of the study treatment that follows a known pattern to the intervention and for which no other explanation is

known. The adverse event, after careful consideration by the investigator, is considered to be possibly related and cannot be ruled out with certainty.

Probable: Any adverse event occurring in a timely manner after the administration of the study treatment that follows a known pattern to the intervention and for which no other explanation is known. The adverse event, after careful consideration by the investigator, is believed with a high degree of certainty to be related to the intervention.

Definitely Related: Any adverse event occurring within a timely manner after administration of the study treatment that is a known sequela of the intervention and follows a previously documented pattern but for which no other explanation is known. The adverse event is believed by the investigator to be incontrovertibly related to the intervention.

Severity

The severity of adverse events will be evaluated using the Common Terminology Criteria for Adverse Events (CTCAE) v4.0 grading scale¹⁵.

Grade 1:	Mild
Grade 2:	Moderate
Grade 3:	Severe
Grade 4:	Life-threatening or disabling
Grade 5:	Death

Grade 1 toxicities such as mild fatigue, nausea, vomiting, skin irritation, pain, loss of appetite and some physical function are common and expected side effects of radiation therapy and therefore should not be reported as adverse events, if the event is documented in the subject's medical record¹⁶. **Only Grade 2 or higher toxicities that are relevant to treatment-related area(s) will be documented as AEs/SAEs for both treatment arms.**

These toxicities must be documented in the AE log and SAE report form, and entered in REDCap, and follow REB and institutional reporting guidelines.

Note: The term “severe” is a measure of intensity: thus a severe adverse event is not necessarily serious. For example, nausea of several hours’ duration may be rated as severe, but may not be clinically serious.

Immediately Reportable Serious/Adverse Events

Any **Grade 4 or 5 serious adverse event** that is definitely, probably, or possibly the result of protocol treatment must be reported to the Study PI within 24 hours of discovery, and

Protocol number v12.0; 16 Apr 2024

further reported to the REB per institutional guidelines. The follow-up/final report should be completed within an additional 8 days. All other SAEs (Grade 2-3) that are definitely, probably, or possibly related to treatment should be reported to the Study PI within 15 days. These should be documented in an SAE Report form and in REDCap as well.

Unanticipated events are to be reported to the Study PI within 24 hours of discovery, and to the local REB as required.

Local and non-local SAEs will be reported to the applicable REB as per their reporting guidelines.

NOTE: Conditions that are NOT considered a SAE in this protocol are not included in reporting requirements, e.g., hospitalizations for routine procedures, disease progression, or death from disease progression

8.3 Follow-up of Subjects after Adverse Events

After the initial AE/SAE report, the investigator is required to proactively follow each subject at subsequent visits/contacts. All SAEs will be followed until resolution, stabilization, the event is otherwise explained, or the subject is lost to follow-up (as defined in Section 11.5).

8.4 Pregnancy

Details of pregnancies will not be collected.

9. Statistics

9.1. Statistical Methods

Patients will be analyzed in the groups to which they are assigned (intention-to-treat). All analyses will be done using t-tests between the average scores of the two arms.

RINV will be assessed via Functional Living Index – Emesis (FLIE) scores compared between the two arms at baseline and day 5 post start of RT

Health-Related Quality of Life (HRQoL) will be measured using the EQ-5D-5L and combined with survival outcomes to explore differences in Quality Adjusted Life Year (QALY) gains or losses between treatments

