2.3. Study Population

Patients with a clinical diagnosis of bone metastases, meeting all inclusion and exclusion eligibility criteria.

3. Trial Design

This is a randomized, multi-centre, pragmatic phase III study in palliative patients with bone metastases. Randomization will be performed on patient-level, meaning that if a patient is treated for multiple bone metastases in the same course, all will receive the same treatment technique. This applies only to bone lesions, as per section 3.2. Any additional lesions to be treated will be at the RO's discretion.

Patients will be stratified by treatment dose of either 8 Gy in a single fraction or 20 Gy in 5 fractions.

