3.2. Entry Procedures

PRE-TREATMENT ASSESSMENT

- ECOG status
- Eligibility according to inclusion and exclusion criteria
- Patient Reported Outcomes
 - Brief Pain Inventory
 - Functional Living Index – Emesis
 - EQ-5D-5L

Entry Procedures

All randomizations will be done using a computer-generated randomization scheme.

All eligible patients enrolled in the study by the participating treatment centre will be assigned a study number, which must be used on all documentation.

The following information will be required:

- Trial code (where applicable)
- Name of investigator under whose name the patient will be randomized
- Informed consent, version date, date signed by patient, name of person conducting consent discussion and date signed by the person who conducted the consent from discussion
- Confirmation that the patient meets the eligibility requirements in Section 4.0 (as per completed Subject Registration Form)

Stratification factors

All metastases lying at least partly within T11-L5 or the pelvis will be treated according to randomization technique, and should receive the same dose (either 8 Gy in 1 fraction or 20 Gy in 5 fractions), chosen pre-randomization. All other bone metastases that need to be treated can be treated with either 20 Gy in 5 fractions or 8 Gy in 1 fraction, can be treated at the same time. Technique for these lesions can be chosen by RO or centre discretion. The total number of fields that can be treated synchronously is 3, and included both eligible and ineligible fields. If additional bone metastases are symptomatic, they can be treated at a later time, no sooner than 4 weeks from the end of radiotherapy on trial.

A description of the measures taken to minimize avoid bias including:

a. Randomization (simple/restricted/blocked/stratified)

Simple randomization with stratification will be used to randomly assign patients to either Arm 1 or Arm 2 in a 1:1 ratio using a computer-generated randomization scheme known only to the trial statistician.

b. Blinded/Unblinded

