4.1. Inclusion Criteria

Subjects must meet all of the following criteria to be eligible for participation in this study:

- Age 18 or older
- Able to provide informed consent
- Clinical diagnosis of cancer with bone metastases (biopsy not required)
- Currently being managed with palliative intent RT to 1-3 RT fields for bone metastases, at least one RT field (PTV) must (at least) partly lie within T11-L5 or pelvis.
- ECOG Performance Status 0-3
- Patient has been determined to potentially benefit from 8 Gy or 20 Gy
- Radiation Oncologist is comfortable prescribing 8 Gy in 1 fraction or 20 Gy in 5 fractions RT for bone metastases
- Negative pregnancy test result for women of child-bearing potential
- The baseline assessment must be completed within required timelines, prior to randomization.
- Patients must be accessible for treatment and follow-up. Investigators must assure themselves the patients randomized on this trial will be available for complete documentation of the treatment, adverse events, and follow-up.
- For simplicity of planning, expected GTV should be less than 20 cm based on radiological or clinical evidence
- Patient must be prescribed a 5-HT3 receptor antagonist (e.g. Ondansetron) as antiemetic prophylaxis prior to RT start.
- Patient is able and willing to complete the quality of life questionnaires, and other assessments that are a part of this study, via paper or using REDCap if they provide their email address on the informed consent

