9.2. Planned Subjects Enrolled

The primary outcome is Functional Living Index – Emesis (FLIE) score compared between the two arms at day 5 post start of RT. We expect patients in the SUPR arm to have a mean FLIE score of 36, 5 days post start of RT¹⁷. We anticipate that VMAT will have a much lower RINV impact (i.e. less decline in FLIE) and for the purpose of this study will hypothesize that the FLIE will be approximately 28. The standard deviation used for sample size calculation was 16.

Sample size was calculated with these FLIE scores. With alpha Type I error set at 0.05 and power set at 0.9, with a dropout rate of 30%, we calculated a conservative sample size of 250 patients. This dropout rate of 30% is a conservative number. We will collect patient demographics and if there is an indication that bias is being introduced because of dropout, we will consult with a statistician.

Our most important secondary outcome (primary efficacy outcome) is radiation induced nausea and vomiting (RINV) which occurs in 60% of patients who receive RT to the lower spine or pelvis^{17, 18}. Using the sample size of 250 patients (see above), this study has a power of 0.8 to detect a 25% difference in RINV (from 60% to 35%) with alpha Type I error set at 0.05 and a dropout rate of 20%. As outlined in the table below, if RINV difference is lower, or higher our power will be lower and higher, respectively.

Health-Related Quality of Life (HRQoL) will be measured using the EQ-5D-5L and combined with survival outcomes to explore differences in Quality Adjusted Life Year (QALY) gains or losses between treatments¹⁹.

Approximate sample size required

RINV 60% to 50% 1600

RINV 60% to 40% 400

Protocol number v12.0; 16 Apr 2024

RINV 60% to 35%	250
RINV 60% to 30%	175
RINV 60% to 20%	90

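### The primary Day 5 FLIE comparison is an unadjusted t-test; adjusting for pre-randomisation FLIE and the dose stratum would be a free gain in precision

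*Combined protocol and SAP*

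**What the plan says.** Section 9.1 gives one method for everything: "All analyses will be done using t-tests between the average scores of the two arms". No section names a covariate, a regression model or a stratified test.

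Both candidate covariates are in hand before allocation:

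- **Baseline FLIE.** It is listed in the pre-treatment assessment (Section 3.2) and marked at Visit 1 in the schedule (Section 4.8). Section 4.1 requires: "The baseline assessment must be completed within required timelines, prior to randomization".
- **Dose.** Section 3 states: "Patients will be stratified by treatment dose of either 8 Gy in a single fraction or 20 Gy in 5 fractions". Section 3.2 describes the method this way: "Simple randomization with stratification will be used to randomly assign patients to either Arm 1 or Arm 2 in a 1:1 ratio".

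On the role of baseline, Sections 3.1.2, 9.2 and 10.1.1 define the primary outcome as the Day 5 score. Section 9.1 also speaks of FLIE "scores compared between the two arms at baseline and day 5 post start of RT", and Section 9.2 explains the expected benefit of VMAT as "less decline in FLIE".

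**The concern.** A baseline measurement of the outcome is often the strongest available predictor of the later value. Leaving it out puts variation between patients that could be explained into the standard error, so the interval for the primary comparison may be wider than it needs to be. Leaving out the stratification factor does the same on a smaller scale. It also leaves any chance imbalance in dose between the arms in the estimate. Simple randomisation and stratification are named together without a balancing mechanism, so balance within stratum cannot be taken for granted.

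The wording on baseline also leaves room for more than one analysis: a Day 5 comparison, a comparison of change, or an additional significance test at baseline. These differ in power, and the choice should not be open when the data are analysed. Precision matters most if the true difference is smaller than the 8 points planned.

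**Working it through.** **Inputs from Section 9.2:** means 36 (SUPR) and 28 (VMAT), so a difference of 8; SD 16; alpha 0.05, taken as two-sided; power 0.90; dropout 30%; N = 250. Section 7 gives a FLIE range of 18 to 126, low being favourable. **Assumed, because not in the documents:** the correlation r between baseline and Day 5 FLIE, and any FLIE difference between dose strata.

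**1. The plan's sample size.** Per arm, n = 2(1.960 + 1.282)² × 16² / 8² = 84.1, so 85; total 170; 170/0.70 = 243. The t-based version gives 86 per arm, 172 in total, and 172/0.70 = 246. The stated 250 reproduces closely; a one-sided alpha would give only 198.

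**2. The planned t-test.** Evaluable patients: 250 × 0.70 = 175, or 87.5 per arm. SE = 16√(2/87.5) = 2.42. Half-width of the 95% interval = 4.77. Power (noncentral t) = 0.908.

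**3. ANCOVA on baseline.** Residual SD = 16√(1 − r²), with two fewer degrees of freedom for the two covariates. The equivalent number of evaluable patients under the t-test is 175/(1 − r²). For comparison, a change-score t-test with the same SD at both times has SD 16√(2(1 − r)). The ratio of ANCOVA to change-score variance is (1 + r)/2, which is below 1 whenever r is below 1.

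| r (assumed) | Residual SD | SE | Half-width | ANCOVA power, 175 | Equivalent N | ANCOVA power, 200 | Change-score power, 175 |
|---|---|---|---|---|---|---|---|
| t-test | 16.00 | 2.42 | 4.77 | 0.908 | 175 | 0.940 | – |
| 0.2 | 15.68 | 2.37 | 4.68 | 0.919 | 182 | 0.949 | 0.739 |
| 0.3 | 15.26 | 2.31 | 4.55 | 0.932 | 192 | 0.958 | 0.794 |
| 0.5 | 13.86 | 2.09 | 4.14 | 0.967 | 233 | 0.982 | 0.908 |
| 0.6 | 12.80 | 1.94 | 3.82 | 0.984 | 273 | 0.993 | 0.957 |

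(The 200 column is 20% dropout, the rate that Section 9.2 uses for the RINV outcome.) For a true difference of 6 points and 175 evaluable, power is 0.694 unadjusted, 0.734 at r = 0.3 and 0.813 at r = 0.5.

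**4. Dose stratum.** Under simple randomisation with an assumed 50:50 dose split, the 95% range for the difference in stratum share between arms is ±1.96√(0.25 × 2/87.5) = ±14.8 percentage points. If the strata differ by an assumed 4 or 8 FLIE points, the unadjusted estimate moves by up to 0.148 × 4 = 0.6 or 0.148 × 8 = 1.2 points. This is chance variation that the standard error already covers, not bias.

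**5. Skewness.** A mean of 28 with SD 16 above a floor of 18 implies skewed scores. A simulation used gamma-distributed scores floored at 18, 88 patients per arm, HC3 robust standard errors and 3,000 runs per setting. ANCOVA type I error was 0.041 to 0.047. Power was 0.914, 0.943 and 0.988 at realised r of 0.26, 0.45 and 0.65, against 0.900 to 0.907 for the t-test. A separate simulation with lognormal scores and 175 patients gave ANCOVA type I error of 0.048 to 0.054.

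**The case against.** The strongest reply is that nothing is broken. The t-test is valid and reaches its planned power, and the benefit of ANCOVA rests on an unknown r. Low r is plausible: many patients may score near the floor of 18 at baseline, and Day 5 nausea is expected to come from the radiation. In a simulation of the proposed model with 4,000 runs per setting, power was 0.894 against 0.898 for the t-test at r = 0, 0.891 against 0.895 at realised r = 0.12, and 0.909 against 0.895 at r = 0.29. All of this stands. It limits the size of the claim and not its direction, because the losses at low r are within simulation error.

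It can also be said that the endpoint is clear: it is defined repeatedly as the Day 5 score, and the sample size uses Day 5 means. The phrase about decline is then a loose aside, since under Section 7 a worsening is a rise in score. That is a fair reading. The change-score figures show only what a different reading would cost.

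The stratum range in step 4 is a worst case. Randomisation is described as stratified; how balance is obtained is unstated, not shown to be absent.

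Finally, a change to the primary analysis this late needs care. Version 12.0 is dated April 2024, and Section 3.3 places an interim analysis around December 2024. That is a condition on the fix. Section 3.2 keeps analysts blinded to arm identity, and Section 9.3 asks that departures from the statistical plan be described and justified.

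**Conclusion.** The point holds as an improvement worth making. The primary analysis uses neither pre-randomisation FLIE nor the stratification factor, although both are already collected. Adjustment cuts the variance by r²: 4% at r = 0.2, 9% at 0.3, 25% at 0.5 and 36% at 0.6. At r = 0.3 to 0.5 this is worth about 17 to 58 extra evaluable patients (192 − 175 and 233 − 175). Stratum adjustment adds less.

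These figures rest on the plan's difference and SD, on 30% dropout and on an assumed r. The worst case is a cost of about 1% in the standard error. There is no bias in the planned test and no shortfall in power.

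Missing Day 5 scores are a side issue and do not carry this conclusion. Section 9.2 says only that "if there is an indication that bias is being introduced because of dropout, we will consult with a statistician", but Sections 4.3 and 5.5 provide for termination assessments and telephone follow-up. For an observed difference of 8 with 30% missing and no shift in the SUPR arm, significance is lost only if missing VMAT scores are (8 − 4.77)/0.3 = 10.8 points worse than those observed. Under the planning means they would then average 38.8, above the SUPR mean of 36. For an observed difference of 6 the shift is 4.1 points.

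**What to change.** Amend Section 9.1 before any comparative result is seen:

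- **Primary analysis:** a linear model of Day 5 FLIE on arm, Visit 1 FLIE and dose stratum, with robust standard errors, reporting the adjusted difference and its 95% interval. Keep the unadjusted t-test as a supportive analysis.
- **Covariate:** use the Visit 1 value and not a repeated Day 1 value. Under Section 4.8 the repeat depends on the wait between baseline and treatment, so it comes after randomisation and may differ by arm.
- **Missing Visit 1 FLIE:** state a rule that does not use arm. The Appendix A checklist omits the baseline-assessment criterion of Section 4.1, so some values may be absent.
- **Baseline:** describe scores by arm and plan no significance test there.
- **Optional additions:** report Day 5 missingness and reasons by arm, with a tipping-point analysis that varies the shift separately by arm. Limit the t-test sentence to continuous scores, and name categorical methods for RINV control, pain response category and time to treatment.

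The cost is a few lines of analysis text and the usual amendment step. It needs no new data, visits or patients, and the sample size can stay at 250.
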